14 PUBLICATION PLAN21
15 REFERENCES.....21

List of Abbreviations

ACEIs	Angiotensin converting enzyme inhibitors
AE	Adverse Event/Adverse Experience
ANP	Atrial natriuretic peptide
ARB	Angiotensin receptor blocker
BNP	Brain natriuretic peptide
CCaTS	Center for Clinical and Translational Science
CFR	Code of Federal Regulations
cGMP	Cyclic guanosine monophosphate
CHF	Congestive Heart Failure
CNP	c-type natriuretic peptide
CRF	Case Report Form
CRTU	Clinical Research and Trials Unit
DSMB	Data and Safety Monitoring Board
EF	Ejection Fraction
ES	Executive Secretary
FDA	Food and Drug Administration
GFR	Glomerular Filtration Rate
GCP	Good Clinical Practice
HF	Heart Failure
HFrEF	Heart Failure with Preserved Ejection Fraction
HFrEF	Heart Failure with Reduced Ejection Fraction
HIPAA	Health Insurance Portability and Accountability Act
HR	Hazard ratio
IB	Investigator's Brochure
IRB	Institutional Review Board
IV	Intravenous
LVEF	Left ventricular ejection fraction
NEP	Neprilysin
NEPi	Neprilysin inhibitor
NP	Natriuretic peptide
NPRC	Natriuretic peptide clearance receptor
NYHA	New York Heart Association

Study Summary

Title	A Proof of Concept Study to Determine the Efficacy of Entresto™ in heart failure with preserved ejection fraction (HFpEF) Based on Circulating Neprilysin Levels: The Circulating NEP and NEPi (CNEPi) Study
Running Title	CNEPi
Protocol Number	IRB # 18-000044
Phase	Phase 4
Methodology	Proof of Concept Study
Overall Study Duration	21 months
Subject Participation Duration	5 weeks
Single or Multi-Site	Mayo Clinic Sites
Objectives	Determine biomarker (plasma NT-proANP, NT-proBNP, NT-proCNP, cGMP) responses to Entresto™ in patients with HFpEF who have high and low serum NEP levels
Number of Subjects	40
Diagnosis and Main Inclusion Criteria	Subjects with NYHA 2-4 HFpEF
Study Product, Dose, Route, Regimen	Entresto™ 49/51 mg (sacubitril/valsartan) orally twice-daily
Duration of Administration	Up to 5 weeks
Reference therapy	NA
Statistical Methodology	Paired t-test comparing the change from baseline to up to 5 weeks after administration of Entresto™

1 Introduction

This document is a protocol for a human research study. This study will be carried out in accordance with the applicable United States government regulations and Mayo Clinic research policies and procedures.

1.1 Background

Heart failure with preserved ejection fraction (HFpEF) can result from abnormalities in the process of active relaxation and passive stiffness of the heart¹. The natriuretic peptides (NPs) play an important role in cyclic guanosine monophosphate (cGMP) mediated inhibition of cardiomyocyte growth, smooth muscle and fibroblast proliferation and collagen deposition that can affect passive stiffness²⁻⁴. Further, NPs can attenuate angiotensin-II, endothelin-1 and arginine-vasopressin induced increased proliferation of vascular smooth muscle cells⁵. HFpEF is characterized by elevated intra-cardiac pressures⁶ and the natriuretic and diuretic properties of NPs play a pivotal role in maintaining normal volume homeostasis^{7, 8}. Natriuretic peptides also reduce peripheral vascular resistance and blood pressure⁹. The NPs additionally inhibit the effects of the renin-angiotensin-aldosterone and sympathetic nervous system¹⁰⁻¹³ the maladaptive activation of which results in the clinical syndrome of HF. Nephilysin (NEP) mediates the anti-fibrotic, anti-proliferative, myocardial relaxation, vasodilator and diuretic properties of NPs by maintaining NP homeostasis. NPs are degraded and cleared by NEP and the NP clearance receptor (NPRC) respectively. NEP inhibition (NEPi) therefore results in significant increases in plasma BNP, urinary BNP and urinary sodium, increases in cardiac output and reduction in intra-cardiac filling pressures¹⁴.

1.2 Preliminary Data

Entresto™, a crystalline complex of a NEPi (sacubitril) and an angiotensin receptor blocker (ARB, valsartan), was recently approved to treat NYHA Class 2-4 patients with HFpEF after the PARADIGM-HF trial was stopped early due to an overwhelming benefit of the drug in reducing all-cause mortality (hazard ratio [HR]: 0.84; p<0.001), CV mortality (HR 0.80; p<0.001), hospitalization for HF (HR 0.79; p<0.001) and in addition reduced the symptoms and physical limitations of HF by 21% (p=0.001)¹⁵. Entresto™ due to its additional NEPi activity could be a promising new therapy for HFpEF. Entresto™ when administered to patients with HFpEF in a phase 2 study resulted in significantly reduced NT-proBNP levels, a surrogate marker of LV wall stress and NEP activity, as compared to being treated with valsartan alone¹⁶. Entresto™ therefore is being tested as treatment for HFpEF in a Phase 3 trial, PARAGON-HF, evaluating its efficacy in reducing CV death and HF hospitalizations as compared to valsartan.

NEP is a cell membrane bound metalloendopeptidase and can be released from the cell surface, resulting in the formation of a circulating peptide that maintains its catalytic activity^{17, 18}. In recent clinical studies, circulating NEP levels were significantly associated with the composite endpoint of cardiovascular death or HF hospitalization (HR 1.17; p=0.001) and cardiovascular death (HR: 1.19; p=0.002) in patients with HF¹⁹. The PARAGON-HF trial includes all-comers with HFpEF; the final data collection will be completed May 2019. It is being increasingly recognized that HFpEF is a disease entity that has considerable phenotypic heterogeneity^{20, 21}. Therefore, targeting all-comers who suffer from a heterogeneous disease process using a single treatment intervention may not result in desirable outcomes as has been evident with multiple prior negative HFpEF trials^{22, 23}. The importance of biomarker based clinical trials that deliver the right drug to the right patient is being increasingly recognized as a useful strategy to limit sample size and decrease costs by enriching such trials with potential responders^{24, 25}. Whether the beneficial effects of Entresto™ therapy are dependent on baseline NEP levels is unknown and is being explored in this study. The **hypothesis** in this proof of concept study is that

subjects with lower NEP levels will not have an equivalent response to Entresto™, a NEPi, as compared to those with higher NEP levels. The **primary endpoint** measured is change in biomarkers with Entresto™ administration that reflect NEP activity and myocardial stress (NT pro-ANP, -BNP, -CNP) and drug action (cGMP). This endpoint has been well validated as a measure of Entresto™ drug response²⁶.

To establish a median value which will be used to categorize subjects recruited for this pilot study into a low and high NEP group we have measured circulating NEP levels in 242 samples from the **RELAX** and **NEAT-HFpEF** studies. The **RELAX study** was a multicenter, double-blind, placebo-controlled, randomized clinical trial of 216 stable outpatients with HFpEF²⁷. **NEAT-HFpEF** was a multicenter, randomized study of 110 outpatients with HFpEF²⁸. The median circulating NEP level in these populations was 1.55 ng/ml (Q1=0.49, Q3=24.99). Therefore subjects with circulating NEP levels of ≤ 1.55 ng/ml will be considered as having low NEP levels and those with values > 1.55 ng/ml will fall into the high NEP level group.

1.3 Dose Rationale and Risk/Benefits

The effect of administering Entresto™ to subjects with “high” or “low” NEP levels will be studied. Favorable response to Entresto™ therapy in these subjects will be assessed by evaluating a change in biomarkers that reflect NEP activity, myocardial wall stress and clinical outcomes (NT-proANP, NT-proBNP, NT-proCNP)²⁹ and reflect efficacy of drug action (cGMP)²⁶. Entresto is FDA approved for use in HFrEF and will be administered as recommended in the drug labeling information as an off label use in HFpEF as 49/51 mg twice-daily.

2 Study Objectives

Primary Objective: To determine biomarker (plasma NT-proANP, NT-proBNP, NT-proCNP and cGMP) responses to Entresto™ in patients with HFpEF who have high and low serum NEP levels.

3 Study Design

3.1 General Design

Study design: This is a proof of concept single arm study that will be performed in the Clinical Research and Trials Unit (CRTU) at the Center for Clinical and Translational Science (CCaTS), Mayo Clinic. 40 subjects with HFpEF will be assigned to Entresto 49/51 mg (sacubitril/valsartan) twice-daily for a total duration of up to 5 weeks of treatment.

3.2 Primary Study Endpoints

The primary endpoint measured is change in biomarkers with Entresto™ administration that reflect NEP activity and myocardial stress (NT pro-ANP, -BNP, -CNP) and drug action (cGMP). This endpoint has been well validated as a measure of Entresto™ drug response.

4 Subject Selection Enrollment and Withdrawal

4.1 Inclusion Criteria

1. Age ≥ 50 years
2. LVEF $\geq 45\%$ assessed by echocardiography, nuclear scan, MRI or left ventriculogram within the past 24 months

3. Current New York Heart Association (NYHA) class 2-4 symptoms of heart failure (HF)
4. Stable medical therapy for 30 days as defined by:
 - a. No addition or removal of ACE, ARB, beta-blockers, calcium channel blockers (CCBs) or aldosterone antagonists
 - b. No change in dosage of ACE, ARBs, beta-blockers, CCBs or aldosterone antagonists of more than 100%
5. Elevated NT-proBNP (>300 pg/ml) or BNP (>200 pg/ml)
6. One of the following within the last 24 months
 - a. Previous hospitalization for HF with radiographic evidence of pulmonary congestion (pulmonary venous hypertension, vascular congestion, interstitial edema, pleural effusion) **or**
 - b. Catheterization documented elevated filling pressures at rest (LVEDP \geq 15 or PCWP \geq 20) or with exercise (PCWP \geq 25) **or**
 - c. Echo evidence of diastolic dysfunction / elevated filling pressures (**at least two**)
 - i. E/A > 1.5 + decrease in E/A of > 0.5 with valsalva
 - ii. Deceleration time \leq 140 ms
 - iii. Pulmonary vein velocity in systole < diastole (PVs<PVd) (sinus rhythm)
 - iv. E/e' \geq 15
 - v. Left atrial enlargement (\geq moderate)
 - vi. Pulmonary artery systolic pressure > 40 mmHg
 - vii. Evidence of left ventricular hypertrophy
 1. LV mass/BSA \geq 96 (♀) or \geq 116 (♂) g/m²
 2. Relative wall thickness \geq 0.43 (♂ or ♀) [(IVS+PW)/LVEDD]
 3. Posterior wall thickness \geq 0.9 (♀) or 1.0 (♂) cm

4.2 Exclusion Criteria

1. History of hypersensitivity or allergy to ACE inhibitors (ACEIs), ARBs, or NEP inhibitors
2. Known history of angioedema to ACE inhibitors (ACEIs) or ARBs
3. Previous LVEF < 40% at any time
4. Systolic blood pressure < 100 mmHg or > 180 mmHg
5. Current acute decompensated HF (exacerbation of chronic HF manifested by signs and symptoms that may require intravenous therapy)
6. Unstable angina, myocardial infarction, stroke, transient ischemic attack, or cardiovascular surgery or urgent percutaneous coronary intervention (PCI) within 3 months of screening or elective PCI within 30 days of entry
7. Significant valvular stenosis or regurgitation (greater than moderate in severity), hypertrophic, restrictive or obstructive cardiomyopathy including amyloidosis, constrictive pericarditis, primary pulmonary hypertension, or biopsy proven active myocarditis
8. Severe congenital heart disease
9. History of heart transplant or with LV assist device
10. Evidence of severe hepatic disease as determined by any one of the following: history of hepatic encephalopathy, history of esophageal varices, or history of porto-caval shunt.
11. Glomerular filtration rate < 20 ml/min/1.73 m² on most recent clinical laboratories*
12. Serum potassium of > 5.5 mEq/dL on most recent clinical laboratories*
13. Concomitant use of aliskiren in patients with diabetes
14. Currently receiving an investigational drug
15. Inability to comply with planned study procedures

- 16. Female subject who is pregnant or breastfeeding
- * Performed within 90 days of enrollment

4.3 Subject Recruitment, Enrollment and Screening

Subjects meeting the inclusion criteria of the study will be recruited at the Mayo Clinic from the Cardiovascular Diseases Clinic, Community Internal Medicine, General Internal Medicine, Mayo Clinic Cardiovascular Disease database, and past participants of HFpEF studies. The Mayo Clinic Life Science System (MCLSS) will aid recruitment for all the protocols. The MCLSS [REDACTED]

[REDACTED] allows identification of patients in real time during an episode of care no matter where (inpatient or outpatient) at Mayo the patients are being seen. [REDACTED]

[REDACTED] The study coordinator will query the system daily for potential candidates, review the integrated electronic medical records and if appropriate, contact the patient's physician to discuss the study and the patient's participation. Patients will then be contacted for personal interview in person, by phone or letter. Informed consent will be obtained at the screening visit during which blood will be drawn for safety laboratories and NEP levels. Subjects will be assigned to a low or high NEP level group based on the levels and it is anticipated that up to 100 subjects will undergo a screening visit to ultimately enroll 40 subjects for the study which will be carried out during Visits 1 and 2. Subjects will receive a reimbursement of \$100 for participation in each visit (Visits 1 and 2) of the study.

4.4 Early Withdrawal of Subjects

If a subject should stop taking study medication for any reason before completing the 5 weeks of study drug dosing, an attempt should be made to restart the study drug at the lowest starting dose when the subject is stable, per physician discretion. If the treating physician decides to stop study medication and start the patient on an ACEI, then a 36 hour wash-out period is required after the last dose of study drug before starting the ACEI.

4.5 When and How to Withdraw Subjects

If subjects experience an adverse reaction to Entresto™ or if disease progression occurs after consent, the Principal Investigator may consider discontinuing study drug treatment.

4.6 Data Collection and Follow-up for Withdrawn Subjects

[figure not shown]
Subjects will complete all study assessments of Study Visit 2 if they have received study drug for at least 2 weeks or more, regardless of whether they have received the full 5 weeks of study drug treatment. The blood collection component of the study assessment will need to occur within 24 hours of drug discontinuation.

5 Study Intervention

5.1 Description

Please see accompanying **Figure**. Study Intervention comprises of eligible HFpEF subjects who have provided informed consent and in whom blood will be collected (screening visit) to measure serum NEP levels and based on these levels will be assigned to a low or high NEP group. These subjects after having blood drawn at Visit 1 for baseline NEP, NT pro-ANP, -BNP,

-CNP and cGMP levels will then receive Entresto™ for up to 5 weeks. They will return in the 5th week for another blood draw to measure NEP, NT pro-ANP, -BNP, -CNP and cGMP levels. At visits 1 and 2 subjects will also provide urine samples for cGMP levels at baseline and post intervention analysis. Blood will also be collected and stored for future transcriptomic,

metabolomic and genomic studies.

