6.1 Screening Visit

Possible study participants will meet with study coordinator to review consent form. Medical history and current medications will be reviewed. Blood will be drawn for baseline serum NEP levels, safety laboratory tests (potassium, creatinine) and pregnancy test if necessary at the CRTU. Dependent on the results of the NEP levels which will be available within 48 hours, subjects will be assigned to a high or low NEP group. If subjects are found to be eligible and are on ACEi or ARBs, subjects will be instructed to withhold these drugs 36 hours before the initiation of treatment with Entresto™ at Visit 1 and throughout the duration of the study while subjects are on Entresto™.

6.2 Visit 1

Visit 1 will occur within 30 days of the Screening Visit. Qualified subjects will be evaluated as outpatients at the CRTU. Interim history, a review of medications, NYHA class assessment and a brief physical exam will be performed by a qualified study team member. Blood will be drawn for serum NEP levels, NT-proANP, NT-proBNP, NT-proCNP, cGMP and a pregnancy test will be performed, if necessary; urine sample will also be collected for cGMP levels. An additional 55 mL blood sample will be collected from subjects, for future transcriptomic, metabolomic and genomic analysis, who provide consent to allow their blood to be stored in the BAP laboratory for future studies. Subjects will be given the option to opt in or out of this component of the study. Following this, subjects will receive their first dose of Entresto™. BPs will be monitored at baseline prior to

administration of Entresto™ and 60 minutes after this first dose to ensure tolerance of the medication. Sitting systolic and diastolic BP will be monitored in the subject's dominant arm 3 times with an automatic blood-pressure monitor (Omron, Bannockburn, IL) and an average reading of these 3 measurements will be used. Before dismissal, subjects will be provided with Entresto™ tablets for the duration of the study. Study coordinator will follow-up with the subject by telephone on day 14 ± 5 post-visit 1 to monitor compliance and to assess tolerance.

6.3 Visit 2

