Upon completion of 4 weeks of drug intervention, during the 5th week of therapy subjects will be admitted as outpatients to the CRTU. Subjects will be asked to take their last dose of Entresto™ prior to their clinical visit. Interim history, a review of medications, NYHA class assessment and a brief physical exam will be performed by a qualified study team member. Baseline sitting systolic and diastolic BP will be monitored in the subject's dominant arm 3 times with an automatic blood-pressure monitor (Omron, Bannockburn, IL) and an average reading of these 3 measurements will be used. Blood will be drawn for serum NEP levels, NT-proANP, NT-proBNP, NT-proCNP and cGMP; urine sample will also be collected for cGMP levels. An additional 55 mL blood sample will also be collected from subjects, for future transcriptomic, metabolomic and genomic analysis, who provide consent to allow their blood to be stored in the BAP laboratory for future studies as in Visit 1.

7 Potential Risks and Adequacy of Protection against Risks

Protections for human subjects of research are required under Department of Health and Human Services (HHS) regulations at 21 CFR parts 50, 56, and 312.

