Schedule of Events Table

Study Activity	Screen	Visit 1 Day 1	Interim Call Day 14±5	Visit 2 Week 5
Study Agent		X		X
Informed consent	X			
History (NYHA Class)	X	X	X	X
Concurrent meds	X	X	X	X
Physical Exam (Ht, Wt, BSA, VS,		X		X
Blood draw	X ^a	X ^b		X ^b
B-hCG	X ^c	X ^c		
Urine collection		X ^d		X ^d

a: Plasma NEP, serum potassium, creatinine if required

- b: Plasma NEP, NT pro-ANP, -BNP, -CNP, and cGMP; Blood for future studies
- c: Serum pregnancy test (women of childbearing potential)
- d. cGMP levels in urine sample

7 Statistical Plan

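### Urine cGMP is specified as a bare level from one untimed sample per visit, so its change may reflect urine dilution as well as cGMP excretion; plasma cGMP is unaffected

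*Combined protocol and SAP*

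**What the plan says.** Section 5.1 introduces the urine measure: "At visits 1 and 2 subjects will also provide urine samples for cGMP levels at baseline and post intervention analysis". Sections 6.2 (Visit 1) and 6.3 (Visit 2) use the same clause, "urine sample will also be collected for cGMP levels", and footnote d of the Schedule of Events gives one urine analyte: "cGMP levels in urine sample". None of these places gives a collection interval, a volume, a urine creatinine or an excretion rate. Creatinine appears only as a screening blood test: "a: Plasma NEP, serum potassium, creatinine if required".

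In 6.2 the Visit 1 urine is collected before the first dose. For Visit 2, 6.3 says "Subjects will be asked to take their last dose of Entresto™ prior to their clinical visit", with no set interval from dose to sample. Statistical Methods (7.2) allows transformation of the changes after their distributions have been inspected, but says nothing about dilution.

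The primary objective (section 2) names plasma markers, including cGMP, and footnote b of the Schedule of Events lists cGMP with the plasma analytes. Section 3.2 names cGMP as the marker of drug action without giving a matrix.

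**The concern.** The concentration in a spot urine sample is the excretion rate divided by the urine flow, so it falls when urine is more dilute even if excretion has not changed. Dilution that varies at random adds noise. Dilution that shifts systematically between the two visits biases the change.

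A shift is plausible here. One sample is before drug and the other on drug. The protocol's own background says that "the natriuretic and diuretic properties of NPs play a pivotal role in maintaining normal volume homeostasis", and adds that NEP inhibition raises urinary sodium. Section 5.6 allows diuretics for congestion, and the 30-day stability rule in 4.1 does not list loop or thiazide diuretics.

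At stake is whether the urine result can be interpreted. The plan gives urine cGMP no stated status, so if it disagreed with plasma cGMP a reader could not tell whether dilution explained the difference or how much weight the urine result should carry.

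**Working it through.** The plan has no urine cGMP figure to reproduce: it gives no expected level, change or variance. The total of 40 in 7.1 comes without an effect size, SD or power, and the point does not depend on it.

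**Inputs from the documents.** One urine sample per visit, the first before dosing and the second on drug (6.2, 6.3); cGMP as the only urine analyte (Schedule of Events); 20 subjects per NEP group (7.1); significance at 0.05 (7.2), taken here as two-sided. All other inputs below are assumptions.

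**Step 1, the identity.** Let g be the fold change in cGMP excretion and f the fold change in urine flow from Visit 1 to Visit 2. The observed concentration ratio is g/f.

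**Step 2, constant excretion (g = 1).** The change in concentration is 1/f − 1:
- f = 1.1: −9.1%
- f = 1.2: −16.7%
- f = 1.3: −23.1%
- f = 1.5: −33.3%

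**Step 3, a true rise (g = 1.4 assumed).** The observed ratio is 1.4/f:
- f = 0.8: 1.75
- f = 1.0: 1.40
- f = 1.2: 1.17
- f = 1.4: 1.00
- f = 1.6: 0.875

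The rise vanishes only when flow is 40% higher, and reads as a fall only beyond that. More concentrated urine at Visit 2 exaggerates it.

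**Step 4, low versus high NEP.** On the log scale the observed contrast is log(gH/gL) − log(fH/fL). Assume gL = 1.2 and gH = 1.6, a true ratio of 1.33.
- Same dilution, fL = fH = 1.3: 1.23 against 0.92, ratio 1.33. The contrast is unchanged, although the low group's own change now reads as a fall.
- fL = 1, fH = 1.33: 1.20 against 1.20, ratio 1.00.
- fL = 1, fH = 1.6: 1.00 against 1.20, ratio 0.83.

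On this scale the contrast is distorted only if the change in flow differs by group. Exact cancellation needs the log scale. With plain differences and equal baselines, a common f of 1.3 shrinks the gap from 1.6 − 1.2 = 0.40 to 0.40/1.3 = 0.31 of baseline, without changing its sign.

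**Step 5, noise.** Suppose dilution varies within a person with coefficient of variation CV, independently at the two visits. The SD of the log change due to dilution is √(2 ln(1 + CV²)), and the variance of the change is multiplied by 1 + SD²/base², where base is the SD of the true log change (0.4 to 0.6 assumed).

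| CV | SD from dilution | Variance ratio, base 0.6 | Variance ratio, base 0.4 |
|---|---|---|---|
| 30% | 0.42 | 1.48 | 2.08 |
| 50% | 0.67 | 2.24 | 3.79 |
| 70% | 0.89 | 3.22 | 5.98 |

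For power, take a true high/low ratio of 1.5, an SD of log excretion change of 0.4, and s as the SD of log flow change. Then SD = √(0.4² + s²), power = Φ(ln 1.5 / (SD√(2/20)) − 1.96), and n per group for 80% power = 2(1.960 + 0.842)² SD² / (ln 1.5)².

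| s | SD | Power at 20 per group | n per group for 80% |
|---|---|---|---|
| 0 | 0.400 | 89% | 16 |
| 0.3 | 0.500 | 73% | 24 |
| 0.5 | 0.640 | 52% | 40 |
| 0.7 | 0.806 | 36% | 63 |

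These figures concern the urine measure only.

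**Step 6, the correction.** Creatinine in the same aliquot is diluted by the same flow. The Visit 2 to Visit 1 ratio of cGMP per creatinine is therefore g/c, where c is the fold change in creatinine excretion. If c is close to 1, the ratio returns g.

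**The case against.** The strongest reply is that this does not reach the primary endpoint. Section 2 says plasma, the Schedule of Events lists cGMP among the plasma analytes and gives urine its own row, and 5.1 introduces urine as an addition. No section gives urine cGMP a decision role. That stands. A reader might infer that the trial's drug-action signal could be hidden or reversed; the documents do not support this, because urine dilution does not touch plasma cGMP.

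The plan is also silent on normalisation rather than against it. The laboratory manual cited in 12.2 is mentioned for plasma specimens and does not settle the matter. So the fair statement is that normalisation is not specified, although the single listed urine analyte and the absence of any urine creatinine or volume point the same way.

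A further temptation is to say that the bias runs against the hypothesis because high-NEP subjects would have more diuresis and so a smaller apparent rise. Nothing in the documents shows a group difference in urine flow, and equal dilution cancels on the log scale. Nor is diuretic use a source of bias in itself: use that is the same at both visits largely cancels within a subject and leaves mainly noise. The support for a flow change in week 5 is thin as well, since the study cited for the urinary effects of NEP inhibition concerns, by its title, acute inhibition in experimental heart failure.

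Finally, every magnitude input is assumed. The top of the variance range combines the least favourable values and supposes that correction removes all dilution variance at no cost. None of this removes the possible bias in the within-group urine change, or the noise, which needs no group difference.

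**Conclusion.** The point holds as a limited one. Followed as written, the plan yields a urine cGMP change that may combine excretion with dilution. The consequence is added noise, possible bias in the within-group change if flow differs between visits, and bias in the low- versus high-NEP log contrast only if the change in flow differs by group.

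The size is unknown. As an illustration, 10% to 50% higher flow at constant excretion lowers the concentration by 9% to 33%. With an assumed 30% to 70% dilution CV and a true-change SD of 0.4 to 0.6, the variance of the log change is about 1.5 to 6 times that of a perfectly corrected measure. These are assumed ranges, not estimates for this trial.

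The primary plasma endpoint is unaffected. This is a cheap improvement to an ancillary measure, not a flaw that threatens the study's main result.

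**What to change.** Measure creatinine on the same Visit 1 and Visit 2 urine aliquots and add it to footnote d of the Schedule of Events and to 5.1. In 7.2, prespecify the urine measure as the log ratio (Visit 2 to Visit 1) of cGMP per creatinine, and label it secondary or exploratory. Fixing the log scale in advance also secures the cancellation of dilution common to both groups.

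In 3.2, write plasma cGMP. This only clarifies the text to match section 2 and does not change the endpoint.

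The cost is 40 subjects × 2 visits = 80 routine assays on samples already planned, plus a few lines of text, with no extra visit or sample. The ratio adds minor assay error and relies on creatinine excretion being similar at the two visits. A timed collection with recorded volume would serve the same purpose, but at more burden to subjects.
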